8.10.2 Screening and Pre-treatment Assessments

Written informed consent for participation in the study must be obtained before performing any study-specific screening tests or evaluations. Informed Consent Forms (ICFs) for enrolled participant and for participants who are not subsequently enrolled will be maintained at the study site.

All screening, and all pre-treatment assessments (related to entry criteria), must be completed and reviewed to confirm that participants meet all eligibility criteria.

[REDACTED]

The Investigator will maintain a screening log to record details of all participants screened and to confirm eligibility or record reasons for screening failure.

An Eligibility Screening Form (ESF) documenting the Investigator's assessment of each screened participant with regard to the protocol's inclusion and exclusion criteria is to be completed by the Investigator and kept at the investigational site.

Screening and pre-treatment assessments will be performed at the time points indicated in the SoA Section 1.3), unless otherwise specified.

8.10.3 Assessments during Treatment

Under no circumstances will participants who enroll in this study and have completed treatment as specified, be permitted to be allocated a new randomization number and re-enroll in the study.

All assessments must be performed as per SoA (see Section 1.3).

8.10.4 Assessments at Study Completion/Early Termination Visit

Participants who complete the study or discontinue from the study early (as described in Section 4.1.4 and Section 7) will be asked to return to the clinic 57 ± 4 days after the dose of study drug for a follow-up visit (see Section 1.3 and Section 8.10.5).

8.10.5 Follow-Up Assessments

Assessments at the follow-up/early termination visit will be performed as indicated in the SoA (see Section 1.3). After the study completion/early termination visit, adverse events should be followed as outlined in Sections 8.3.1 and 8.3.3.

9. STATISTICAL CONSIDERATIONS

9.1 SAMPLE SIZE DETERMINATION

The maximum number of participants to be randomized was chosen based on practical clinical judgment. Thirty-six participants are expected to be enrolled in this study. Additional participants will be enrolled in [REDACTED] with the maximum number of participants not exceeding 60. A minimum of 4 active treatment and 2 placebo participants will be included in the first two dose levels. Starting at dose level 3 a minimum of 6 active treatment and 2 placebo participants will be included.

The number of participants may be adapted during the study to characterize precisely the safety and PK profile of RO7126209.

The current planned study design and sample size complies with standard safety review rules applied in single ascending dose studies.

9.2 POPULATIONS FOR ANALYSES

For purposes of analysis, the following populations are defined in [Table 9](#).

Table 9 Analysis Populations

Population	Description
Safety	All participants randomized to study treatment and who received at least one dose of the study treatment, whether prematurely withdrawn from the study or not, will be included in the safety analysis.
Pharmacokinetic	All participants who have received active (RO7126209) treatment will be included in the PK analysis population. Participants will be excluded from the PK analysis population if they significantly violate the inclusion or exclusion criteria, deviate significantly from the protocol, or if data are unavailable or incomplete which may influence the PK analysis. Excluded cases will be documented together with the reason for exclusion. All decisions on exclusions from the analysis will be made prior to database closure.
Immunogenicity	Participants who had at least one predose or at least one post dose ADA assessment will be included and analyzed according to the treatment they actually received. The relationship between ADA status and safety, PK, and biomarker endpoints will be analyzed and reported descriptively via subgroup analyses.

9.3 STATISTICAL ANALYSES

9.3.1 Demographics and Baseline Characteristics

Demographic and other baseline characteristics of the safety analysis population will be listed and summarized with descriptive statistics.

9.3.2 Safety Analyses

All safety analyses will be based on the safety analysis population.

Table 10 Safety Statistical Analysis Methods

Endpoint	Statistical Analysis Methods
Adverse events	The original terms recorded on the eCRF by the Investigator for adverse events will be coded by the Sponsor. Adverse events will be summarized by mapped term and appropriate thesaurus level.
Clinical laboratory tests	All clinical laboratory data will be stored on the database in the units in which they were reported. Laboratory test values will be presented in International System of Units (SI units; Système International d'Unités) by individual listings with flagging of abnormal results. See Appendix 4 for details on standard reference ranges and data transformation and the definition of laboratory abnormalities.
Vital signs	Vital signs data will be presented by individual listings with flagging of values outside the normal ranges and flagging of abnormalities. In addition, tabular summaries will be used, as appropriate.
ECG data analysis	ECG data will be presented by individual listings. In addition, tabular summaries will be used, as appropriate.
Concomitant medications	The original terms recorded on the participants' eCRF by the Investigator for concomitant medications will be standardized by the Sponsor by utilizing a mapped term and appropriate drug dictionary level. Concomitant medications will be presented in summary tables and listings.

9.3.3 Pharmacokinetic Analyses

All PK Analyses will be carried out on the PK analysis population.

9.3.3.1 Plasma Pharmacokinetic Parameters

Plasma PK parameters of RO7126209 will be read directly from the plasma concentration versus time profiles or calculated by using standard non-compartmental methods.

Pharmacokinetic parameters of RO7126209 will include (if appropriate):

- C_{end} : observed plasma concentration at the end of the infusion
- AUC_{0-24h} : Area under the plasma concentration versus time curve from zero to 24 h postdose
- AUC_{0-168h} : Area under the plasma concentration versus time curve from zero to 168h postdose
- AUC_{0-last} : Area under the plasma concentration versus time curve from zero to the last measurable concentration
- AUC_{0-inf} : Area under the plasma concentration versus time curve extrapolated to infinity

- λ_z : Terminal rate constant calculated by linear regression of the log-transformed terminal part of the concentration time curve
- $T_{1/2}$: Apparent terminal half-life, computed as $\ln(2)/\lambda_z$
- CL : the total body clearance calculated as Dose/AUC
- V: Volume of distribution at steady-state, estimated based on iv data using the following formula $V = MRT * CL$, where MRT is the mean residence time and CL total body clearance. Mean residence time is calculated as follows :
 $MRT = (AUMC_{0-inf} / AUC_{0-inf}) - t_{infusion}/2$, where $t_{infusion}$ is the infusion duration

9.3.3.2 CSF Pharmacokinetic Parameters

Population pharmacokinetic analyses using non-linear mixed effects modeling will be performed to analyze the plasma and the CSF concentration data of RO7126209 following IV administration.

The results of this analysis will be reported in a document separate from the clinical study report.

9.3.3.3 Statistical Analyses

The following statistical analysis on the PK parameters ($AUC_{0-\infty}$, [or if it cannot properly be determined AUC_{0-t} or AUC_{0last}] and C_{max}) will be performed after completion of the study to explore dose-proportionality. The following linear model will be applied to the log-transformed, dose-normalized pharmacokinetic study variables:

$$y_{ij} \sim \mu + \lambda_j + \varepsilon_{ij} \quad (i=1,2,\dots,N; j=1,2,\dots,M)$$

where M is the number of different doses, N is the total number of participants, μ denotes the general mean of the transformed variables, λ_j is the effect of dose j and ε_j is the residual error for participant i in the dose level j . The residual errors are assumed to be independent and identically distributed following a normal distribution with zero mean and variance σ^2 .

Least square means with corresponding 90% confidence intervals (CI) will be derived for each dose level and plotted to evaluate if there are obvious trends for normalized PK parameters of decreasing/increasing with dose.

The following hypothesis will be tested (in an exploratory sense) for the primary pharmacokinetic parameters:

H_0 : There is no deviation from dose-proportionality (i.e., $\lambda_1 = \lambda_2 = \dots = \lambda_M$)

versus

H_1 : There is a deviation from dose-proportionality ($\lambda_1 \neq \lambda_2$ for some i, j).

All p values will be interpreted in an exploratory sense only.

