[REDACTED]. Participants will receive a single IV dose of either RO7126209 or placebo. A minimum of 4 active treatment and 2 placebo participants will be included in the first two dose levels. Starting in dose level 3, and in all subsequent cohorts, a minimum of 6 active treatment and 2 placebo participants will be included. Based upon the review of emerging data there will be the option to adjust the number of participants on active treatment or placebo per dose level. If a dose level is repeated or if a lower dose is investigated, the added group will consist of at least 2 participants on active treatment and 1 on placebo.

RO7126209 doses will be administered in ascending order, starting with a dose of 0.1 mg/kg that is expected to be well tolerated. Subsequent doses will be selected in an adaptive manner during study conduct based on emerging safety, tolerability and PK data. A Bayesian adaptive design using the continual reassessment method (CRM) for predicting anticipated maximum dose-limiting events (DLE) rate to guide dose effect relationship will also be applied for dose escalation.

Intermediate dose escalation steps other than those anticipated may be used, doses may be repeated or adjusted based on safety, tolerability and pharmacokinetic data at each dose level, as well as on model-based prediction of the anticipated maximum DLE rate.

In each dose group, sentinel dosing will be employed to allow for an evaluation of safety data by the Investigator up to 48 hours following intravenous administration of RO7126209 or placebo before subsequent participants are dosed. Therefore, the participants will be divided into two groups: 2 participants will be dosed one day (sentinel group with 1 on active treatment and 1 on placebo) and the remaining participants of that dose group no earlier than 72 hours after the first dosing occasion.

There will be at least 2 weeks between each dose level in order to permit adequate time for collation and review of emerging data before the next dose is administered.

The participants, investigators, and site personnel (except site personnel responsible for study drug accountability, reconciliation, record maintenance and drug preparation) will be blinded to treatment assignments.

Participants in the sentinel group will receive a single IV infusion of study medication (RO7126209 or matching placebo) [REDACTED].

No food will be permitted from 2 hours prior to dosing until 4 hours after start of infusion on Day 1.

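### Section 9.3.3.3 looks for a rising or falling trend in dose-normalised exposure but plans no single estimate of departure from dose proportionality; a power-model slope with its 90% CI would be a cheap addition

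*Combined protocol and SAP*

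**What the plan says.** Section 9.3.3.3 sets out the dose-proportionality analysis, run after the study is complete on AUC and Cmax: "The following linear model will be applied to the log-transformed, dose-normalized pharmacokinetic study variables". The model has a general mean, one effect per dose and a residual, "where M is the number of different doses". Least-squares means with 90% CIs are derived for each dose and "plotted to evaluate if there are obvious trends for normalized PK parameters of decreasing/increasing with dose". A global hypothesis that all dose effects are equal is then tested, with the qualification "All p values will be interpreted in an exploratory sense only".

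The section contains no log-dose term, slope or stated contrast between doses, and no interval for the departure. None appears elsewhere in the readable text. Section 9.3.3.2 commits to population PK modelling of plasma and CSF concentrations, reported outside the clinical study report, and does not mention dose proportionality.

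The number of doses is not fixed. The Synopsis says "Intermediate dose escalation steps other than those anticipated may be used", and where a dose is repeated or a lower one investigated, "the added group will consist of at least 2 participants on active treatment and 1 on placebo". Section 4.1.2 also leaves room for doses above the planned range.

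**The concern.** The section asks a directional question, whether normalised exposure goes up or down with dose, and answers it with tools that ignore the order of the doses. The omnibus test spreads its power over every possible pattern (4 numerator degrees of freedom at five doses), and the direction is left to the reader's eye. The clinical study report would carry five means and one p value per parameter, but no statement such as: exposure rises by this factor over the dose range, give or take so much.

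Little is at stake. Dose proportionality is not an objective or endpoint in Section 3, the p values are exploratory, and no dose decision depends on the result. What would be lost is a usable summary for whoever plans the next study.

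**Working it through.** **Inputs from the documents.** Planned doses are 0.1, 0.3, 0.9, 2.7 and 5.4 mg/kg (Section 4.1.2), a 54-fold range. Minimum active participants per dose are 4, 4, 6, 6 and 6 (Section 9.1). The PK population is active participants only (Table 9).

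**The plan's own figure.** 2 × (4 + 2) + 3 × (6 + 2) = 36, which matches the expected enrolment. Active: 4 + 4 + 6 + 6 + 6 = 26. Section 9.1 gives no power or precision for PK, so there is nothing further to reproduce.

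**Assumed.** The readable text gives no between-participant CV, so I take 20%, 30% and 40%, with σ = √ln(1 + CV²) = 0.198, 0.294 and 0.385. The plan sets no alpha. I use 0.10 to match its 90% CIs and show 0.05 as well. No PK exclusions are assumed.

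**Precision of the slope.** Model: ln(parameter) = a + b·ln(dose). The mean of ln(dose) is 0.0546, so Sxx = 22.23 + 6.34 + 0.15 + 5.29 + 15.98 = 49.98 (rounded terms sum to 49.99). The half-width of the 90% CI is t(0.95; 24)·σ/√Sxx. At CV 30% this is 1.711 × 0.2936/7.07 = 0.071, and 54^0.071 = 1.33. For comparison, the ratio of the two end LS means (n = 4 and n = 6) has CI factor exp(t(0.95; 21)·σ·√(1/4 + 1/6)), which at CV 30% is exp(1.721 × 0.2936 × 0.6455) = 1.39.

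**Power for a log-linear departure.** With b = 1.10 the ratio over the range is 54^0.10 = 1.49. The noncentrality is 0.10² × 49.98/σ², which is 5.80 at CV 30%. The factor test uses F(4, 21) and the slope test F(1, 24).

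| Assumed CV | Half-width of b | Factor over range: slope | Factor over range: two end LS means | Power, alpha 0.10: factor test / slope | Power, alpha 0.05: factor test / slope |
|---|---|---|---|---|---|
| 20% | 0.048 | 1.21 | 1.25 | 84% / 97% | 73% / 93% |
| 30% | 0.071 | 1.33 | 1.39 | 51% / 76% | 37% / 64% |
| 40% | 0.093 | 1.45 | 1.53 | 34% / 56% | 22% / 42% |

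**Other shapes.** Each is a 1.49-fold step at CV 30% and alpha 0.10. The slope's power comes from 60,000 simulated trials.

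| Shape | Factor test | Slope |
|---|---|---|
| Two lowest doses low | 75% | 83–84% |
| Lowest dose alone low | 54% | 51% |
| Top dose alone high | 67% | 51% |
| Both end doses high | 79% | 5% |
| Middle dose alone high | 67% | 6% |

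In the last two rows the expected b is about 1.00 and 0.99, so the slope alone would look like proportionality.

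**If doses are added.** These cases are illustrative, at CV 30%, alpha 0.10 and b = 1.10. Two interior doses with 2 active each (N = 30, seven doses): factor test 45%, slope 77%. Two more active at 5.4 mg/kg: factor test 56%. Six active at 10.8 mg/kg, the top of the Appendix 6 grid: factor test 66%.

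**The case against.** The strongest reply is that this is a preference. A factor model, LS means with CIs and a global test form a coherent exploratory analysis, and the test matches the hypothesis as written. That stands: nothing planned is wrong, and a reader who inferred that the model or test is invalid would go further than the text allows.

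Second, the precision gain is small (1.33 against 1.39 at CV 30%). A linear contrast inside the planned model would have 75% power against the slope's 76%. Both figures are right. But the plan states no such contrast either, so the missing summary remains whichever route is used.

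Third, 51% against 76% assumes an exactly log-linear departure, the slope's best case, and the documents do not say what shape to expect. This also stands. It is why the slope should sit beside the planned outputs and not replace them.

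Two stronger readings are tempting. One is that the adaptive design will erode the factor test. Interior doses with few participants can do so, but repeated doses leave the number of levels unchanged and a higher dose can raise power, as shown above. The other is that the fallback from AUC to infinity, "or if it cannot properly be determined", would create a false trend with dose. The wording may mean one switch for everyone, and any size would rest on a half-life and an assay limit that cannot be read in the public documents. That reading is not supported.

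Finally, the population PK model may quantify non-linearity, but the plan neither names dose proportionality there nor puts the result in the clinical study report.

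**Conclusion.** The gap is real and of low priority. Section 9.3.3.3 looks for a trend but provides no single estimate of departure with an interval. A slope would estimate the top-to-bottom ratio of normalised exposure to within a factor of about 1.2 to 1.45. For a steady 1.49-fold departure it would have 13 to 25 percentage points more power than the factor test at alpha 0.10. These figures rest on an assumed CV of 20% to 40%, the tentative doses, the minimum cohort sizes with no exclusions, and log-linearity. The absence of an estimate depends on none of these. The result does not show that the planned analysis is wrong, or that the slope is better for every pattern.

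**What to change.** In Section 9.3.3.3, keep the LS means with 90% CIs, the plot and the exploratory factor test. Add the power model ln(parameter) = a + b·ln(dose) on the untransformed-for-dose parameter, where b = 1 is proportionality. Report b with its 90% CI and the implied ratio over the range actually tested, range^(b − 1), with its CI. State that b is read together with the LS means and the factor test, and that b near 1 is not taken as proportionality if the test or plot shows a non-linear pattern.

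The cost is two or three sentences and one regression per parameter on values already computed, with no extra participants or samples. The downside is the log-linearity assumption, which the retained outputs guard against.

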9.3.5 Immunogenicity Analyses

The immunogenicity analyses will include all participants with at least one ADA assessment, irrespective of whether or not the participant receives any treatment ([Shankar et al 2014](#)).

The numbers and proportions of ADA-positive participants and ADA-negative participants at baseline (baseline prevalence) and after study drug administration (post-baseline incidence during both the treatment and follow-up periods) will be summarized.

- Participants are considered to be ADA positive if they are ADA negative at baseline but develop an ADA response following study drug administration (treatment-induced ADA response), or if they are ADA positive at baseline and the titer of one or more post-baseline samples is greater than the titer of the baseline sample by a scientifically reasonable margin such as at least 4-fold (treatment-enhanced ADA response).

- Participants are considered to be ADA negative if they are ADA negative at baseline and all post-baseline samples are negative, or if they are ADA positive at baseline but do not have any post-baseline samples with a titer that is greater than the titer of the baseline sample by a scientifically reasonable margin such as at least 4-fold (treatment unaffected).

The relationship between ADA status and safety, efficacy, PK, and biomarker endpoints will be analyzed and reported descriptively via subgroup analyses.

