1.3 SCHEDULE OF ACTIVITIES

The schedule of the activities is provided in [Table 1](#) and [Table 2](#).

Table 1 Overall Schedule of Activities

Assessment	Screening ^a																Follow-Up
	Day -56/-3	Day -2	Day -1	Day 1	Day 2	Day 3	Day 4	Day 5	Day 6	Day 7	Day 8	Day 10	Day 15±1	Day 22±1	Day 29±2	Day 43±3	Day 57±4
Time relative to dose (h)	NA	NA	NA	0	24	48	72	96	120	144	168	NA	NA	NA	NA	NA	NA
Written Informed Consent	✓																
Inclusion/Exclusion Criteria	✓	✓															
Brain MRI ^l	✓									✓							✓
Demographics	✓																
Medical History	✓																
Medication History	✓	✓															
Physical Examination ^b	✓	✓															✓
Vital Signs ^c	✓	✓		✓	✓	✓	✓	✓	✓	✓	✓	✓	✓		✓	✓	✓
Respiratory rate ^j		✓		✓	✓	✓					✓						
12-lead ECG ^d	✓	✓		✓	✓		✓		✓		✓	✓	✓		✓	✓	✓
Neurological Examination	✓	✓		✓	✓	✓	✓		✓		✓		✓		✓		✓
Full hematology	✓	✓			✓			✓			✓		✓		✓		✓
Full Blood	✓ ^q	✓			✓						✓		✓		✓		✓

Assessment	Screening ^a																Follow-Up
	Day -56/-3	Day -2	Day -1	Day 1	Day 2	Day 3	Day 4	Day 5	Day 6	Day 7	Day 8	Day 10	Day 15±1	Day 22±1	Day 29±2	Day 43±3	Day 57±4
Time relative to dose (h)	NA	NA	NA	0	24	48	72	96	120	144	168	NA	NA	NA	NA	NA	NA
Chemistry																	
Urinalysis ^e	✓	✓			✓		✓						✓		✓		✓
Serology ^f	✓																
Cerebral spinal fluid			✓ ⁿ			✓ ^o		✓ ^o									
Coagulation	✓	✓				✓ ^o		✓ ^o									✓
Alcohol Test	✓	✓															
Drugs of Abuse	✓	✓															
In-house Period		←----->															
Randomization				✓													
Standard Meal ^g		✓	✓	✓	✓	✓	✓	✓	✓	✓	✓	✓					
Drug Administration				✓													
Pharmacokinetic				✓	✓	✓	✓	✓			✓	✓	✓	✓	✓	✓	✓

Assessment	Screening ^a																Follow-Up
	Day -56/-3	Day -2	Day -1	Day 1	Day 2	Day 3	Day 4	Day 5	Day 6	Day 7	Day 8	Day 10	Day 15±1	Day 22±1	Day 29±2	Day 43±3	Day 57±4
Time relative to dose (h)	NA	NA	NA	0	24	48	72	96	120	144	168	NA	NA	NA	NA	NA	NA
Sampling (Blood) ⁱ																	
Infusion-related reaction blood sample				✓	←-----→												
Previous and concomitant Medications	←-----→																
Adverse Events ^h	←-----→																
Anti-RO7126209 Antibodies				✓							✓					✓	✓ ^p

- a) Safety tests can be repeated once during screening period at discretion of the Investigator.
- b) A complete physical examination will be performed at screening (including height and weight), and abbreviated physical examinations at all other visits (including weight).

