- c) Includes single measurements of systolic and diastolic blood pressure, pulse rate and body temperature. All measurements to be taken after the participant has rested in a supine position for at least 5 minutes.
- d) Triplicate 12-lead ECGs (within 5 minutes) will be measured after the participant has rested in a supine position for at least 10 minutes.
- e) Dipstick analysis of protein, blood, glucose, pH and leukocytes.
- f) Hepatitis B, C, HIV 1 and 2.

Table 1 Overall Schedule of Activities (cont.)

- g) Participants will have to be fasted (water consumption is permitted) for at least 10 hours prior to full panel biochemistry laboratory safety tests (with the exception of screening and follow-up where a fasting period of 4 hours is sufficient). On Day 1, no food is permitted from 2 hours prior to dosing until 4 hours after start of the infusion. On all other days of the in-house period, standard breakfast, lunch, dinner and snack will be provided up to discharge, at the times deemed convenient by the clinical site.
- h) Intensity of adverse events will be graded on a five-point scale (Grade 1, Grade 2, Grade 3, Grade 4 and Grade 5) based on the NCI CTCAE (v5), which can be found at:
https://ctep.cancer.gov/protocoldevelopment/electronic_applications/docs/CTCAE_v5_Quick_Reference_8.5x11.pdf
- i) The Sponsor may decide to terminate PK sampling earlier and/or timing of PK sampling may be modified based on emerging PK data (e.g., consecutive postdose PK samples with below the limit of quantification [BLQ] concentration).
- j) Respiratory rate to be measured after the participant has rested in a supine position for at least 5 minutes.

█ [REDACTED]

█ [REDACTED]

[REDACTED]

█ [REDACTED]

- o) Participants will be randomized to two subgroups per dose group. One subgroup will have the CSF sampling on Day 3, the other subgroup on Day 5. The safety biomarker (blood) and coagulation sample will be taken accordingly.
- p) In case of ADA positive results at follow-up visit, the participant will be asked to come back to the unit monthly for additional ADA testing until *this is no longer clinically indicated (see Section 8.7)*. At each visit a corresponding PK sample must be also taken.

Table 1 Overall Schedule of Activities (cont.)

■	[REDACTED]
■	[REDACTED]
■	[REDACTED]
■	[REDACTED]
■	[REDACTED]

Table 2 Specific Schedule of Assessments

Procedure	Day -2	Day -1	Day 1												Day 2
			Nominal Time												

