
 • To investigate the single intravenous dose pharmacokinetics (PK) of RO7126209 in plasma of healthy participants • To investigate the CSF penetration after a single dose of RO7126209 in healthy participants • To evaluate the immunogenicity of a single dose of RO7126209 in healthy participants 	
 • Plasma PK parameters of RO7126209 • CSF concentration of RO7126209 • Incidence of anti-RO7126209 antibodies (ADAs)
Exploratory	

 • To explore PK/safety relationships of RO7126209 in healthy participants 	
 • Relationship between plasma exposure of RO7126209 and safety measurements

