Appendix 4 Clinical Laboratory Tests

The tests detailed in [Table 1](#) will be performed by the central or local laboratory. The results will be entered into the eCRF or loaded electronically.

Protocol-specific requirements for inclusion or exclusion of participants are detailed in Sections [5.1](#) and [5.2](#), respectively, of the protocol.

Additional tests may be performed at any time during the study as determined necessary by the Investigator or required by local regulations.

Table 1 Protocol-Required Safety Laboratory Assessments

Laboratory Assessments	Parameters
Full Hematology	
 [REDACTED]
[REDACTED]	
 [REDACTED]
Full Clinical Blood Chemistry	
 ALT, AST, ALP, GGT, total, direct and unconjugated bilirubin, total protein, haptoglobin, albumin, sodium, chloride, potassium, phosphate, calcium, creatinine, urea, fasting glucose, total cholesterol, triglycerides, CPK, LDH, [REDACTED]
[REDACTED]	
 [REDACTED]
Coagulation	
 Prothrombin time (INR) and activated thromboplastin time (APTT).
Viral Serology	
 HIV (specific tests HIV1 antibody, HIV-1/2 antibody, HIV-2 antibody), hepatitis B surface antigen (HBsAg), hepatitis C virus (HCV) antibody.
Safety Biomarkers	
 [REDACTED] [REDACTED]

Laboratory Assessments	Parameters
Infusion-related reaction blood sample	
 • [REDACTED]
Thyroid Hormones	
 • Thyroid stimulating hormone (TSH) at screening only
Anti-Drug Antibodies	
 • Anti-RO7126209 antibodies in plasma will be determined using a validated ELISA method
Urinalysis	
 • Dipstick: pH, glucose, blood and protein. If there is a clinically significant positive result (may be confirmed by a positive repeated sample), urine will be sent to the laboratory for microscopy and culture. If there is an explanation for the positive dipstick results, it should be recorded and there is no need to perform microscopy and culture. • Microscopic examination (sediment, RBCs, WBCs, casts, crystals, epithelial cells, bacteria), if blood or protein is abnormal.
Alcohol	
 • Urine

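### Section 9.3.5 classes participants as ADA negative without checking the drug level in the sample, so masking at higher doses could go unseen

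*Combined protocol and SAP*

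**What the plan says.** Table 3 makes the incidence of anti-RO7126209 antibodies a secondary endpoint. Section 9.3.5 gives two classes. For a participant negative at baseline, the rule is: "Participants are considered to be ADA negative if they are ADA negative at baseline and all post-baseline samples are negative". For a participant positive at baseline, the class depends on the change in titre. Neither branch refers to the drug concentration in the sample, and there is no inconclusive class. The same section adds: "The relationship between ADA status and safety, efficacy, PK, and biomarker endpoints will be analyzed and reported descriptively via subgroup analyses". It states no stratification by dose.

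On the assay, Appendix 4 says: "Anti-RO7126209 antibodies in plasma will be determined using a validated ELISA method". No drug-tolerance limit is visible there.

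As the ticks in Table 1 of Section 1.3 read, ADA is sampled predose on Day 1 and on Days 8, 43 and 57, with PK blood on each of those days. Footnote p extends follow-up only for positives: "In case of ADA positive results at follow-up visit, the participant will be asked to come back to the unit monthly". For those extra visits it adds: "At each visit a corresponding PK sample must be also taken". Footnote i allows PK sampling to be cut: "The Sponsor may decide to terminate PK sampling earlier and/or timing of PK sampling may be modified based on emerging PK data".

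**The concern.** RO7126209 still in plasma can bind ADA and hide it from the assay. A negative result is then informative only when drug in that sample is within the assay's tolerance. The visible rule takes every negative at face value. Drug level rises with dose, so any false negatives would tend to gather at the top dose levels.

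Two results would suffer. Incidence by dose would be too low at the higher doses. In the ADA-PK subgroups, masked positives would sit in the negative group and shrink any ADA-related difference in exposure. In addition, a participant masked at Day 57 would not trigger the monthly follow-up in footnote p, so no later sample would correct the class.

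**Working it through.** **Denominators.** Section 9.1 gives 4 + 2 participants at dose levels 1 and 2, and 6 + 2 at levels 3 to 5. 2 × 6 + 3 × 8 = 36, which reproduces the planned enrolment: 26 active (4 + 4 + 6 + 6 + 6) and 10 placebo.

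**Dose range.** Section 4.1.2: 5.4 / 0.1 = 54. Under linear PK the top dose needs log2(54) = 5.75 more half-lives than the lowest to reach the same concentration. That is about 40 days at an assumed half-life of 7 days and 81 days at 14 days.

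**Drug level at the ADA samples.** The projected PK is redacted, so everything here is assumed: 75 kg, bolus, two compartments, V1 = V2 = 3 L, Q = 0.6 L/day, CL = 0.25, 0.6 or 1.5 L/day. Let k10 = CL/V1 and k12 = k21 = 0.2 per day, with rates a > b satisfying a + b = k10 + k12 + k21 and ab = k10 × k21. Then C(t) = (Dose/V1) × [(a − k21)e^(−at) + (k21 − b)e^(−bt)] / (a − b). Days 8, 43 and 57 are t = 7, 42 and 56 days. Concentrations are in ug/mL.

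| Terminal half-life | 0.1 mg/kg, Day 8 | 5.4 mg/kg, Day 8 | 5.4 mg/kg, Day 43 | 5.4 mg/kg, Day 57 |
|---|---|---|---|---|
| 18.5 days | 0.83 | 45 | 11.2 | 6.6 |
| 9.1 days | 0.45 | 24 | 1.5 | 0.52 |
| 5.3 days | 0.12 | 6.5 | 0.06 | 0.01 |

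**Against an assumed tolerance of 1 to 5 ug/mL.** On Day 8, the top dose is above it in all three cases and the lowest dose in none. Day 8 is not decisive, however, because one later unmasked positive makes a baseline-negative participant positive. What matters for someone who completes is Day 57. Only the 18.5-day case exceeds the tolerance there: at 5.4 mg/kg for any tolerance in the range, at 2.7 mg/kg (3.3) for a tolerance below 3.3, and at 0.9 mg/kg (1.1) only for a tolerance close to 1.

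**Sensitivity to the model.** With one compartment and V = 50 mL/kg, C = (Dose/V) × 2^(−t/half-life). At Day 57 and 5.4 mg/kg this gives 0.42, 2.2, 6.8 and 17 ug/mL for half-lives of 7, 10, 14 and 21 days. For a half-life of 7 days or less, no dose exceeds 1 ug/mL at Day 57. At a tolerance of 100 ug/mL nothing is masked on any ADA day. The half-life at which Day 57 becomes a problem therefore depends on the model as well as on the tolerance.

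**Possible size.** Suppose true incidence is 30% at every dose and half of the ADA in the top two levels is masked. Observed incidence there is 0.30 × 0.5 = 15%. Over all active participants it is (0.30 × 14 + 0.15 × 12) / 26 = 23.1%. With no masking it is 30%, and with complete masking in those two levels 0.30 × 14 / 26 = 16.2%.

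Now suppose ADA halves AUC within a dose group, with 30% incidence and 50% masking. The masked share of the negative group is 0.15 / (0.70 + 0.15) = 0.176. The geometric mean ratio then reads 0.5 / 0.5^0.176 = 0.565 instead of 0.50.

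**The case against.** A reader might infer that ADA incidence and the ADA-PK comparison are biased with dose. The documents do not support that. It would require the half-life, the volume of distribution and the assay's tolerance, and none is visible. Blocks of Section 8.7, the assay section, are redacted, and a tolerance figure or an interpretation rule may stand there. A participant is misclassified only if every sample containing ADA is masked. In two of the three two-compartment cases, no dose exceeds 1 ug/mL at Day 57. Footnote i itself foresees consecutive samples below quantification. All of this stands.

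A reader might also infer that the ADA-negative group will look like the high-exposure group. That needs raw exposure pooled over doses, which Section 9.3.5 does not state. Within a dose the effect is dilution.

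The consequence is limited too. ADA is a secondary, descriptive endpoint, and Section 8.7 says ADA data are not required for dose escalation. With 6 active participants and 10% true incidence, the chance of seeing no positive is 0.9^6 = 53% without any masking, so a dose trend is hard to read in any case.

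What the objection does not remove is the rule itself. Section 9.3.5 is shown in full and uses no drug level, so a tolerance figure in Section 8.7 would not by itself change how it classifies a negative. Nor does every route need a long half-life. Section 8.10.4 asks early leavers to return at Day 57, but Section 7.2 ends follow-up once consent is withdrawn. A participant who withdraws consent after Day 8 would be classed on that sample alone.

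**Conclusion.** The point holds as a risk. The visible rule cannot separate a credible negative from one read in the presence of drug, and the 54-fold dose range makes the second kind likelier at the higher doses. If masking occurs, incidence there is biased downward and the ADA-PK contrast within a dose is diluted.

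The size runs from nothing to material: no effect with a short half-life or a high tolerance, and up to the top three dose levels at Day 57 with a long half-life and a tolerance near 1 ug/mL. In the two-compartment scenarios only a half-life of about 18 days leaves Day 57 above a tolerance of 1 to 5 ug/mL. Participants whose last sample is early are exposed whatever the late concentrations. All concentrations, tolerances and masking fractions are assumptions. This is a cheap improvement to a secondary-endpoint rule.

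**What to change.** In Section 9.3.5, cite the ELISA's validated drug tolerance. Flag as *ADA negative, drug above tolerance (inconclusive)* any participant with no positive post-baseline sample whose last ADA sample has a paired RO7126209 concentration above that tolerance. Then:

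- Keep all evaluable participants in the denominator. Report ADA incidence by dose with inconclusives counted first as negative and then as positive.
- Run the ADA-PK subgroup comparison within dose or on dose-normalised exposure, with inconclusives shown as a separate group.
- Keep the PK sample paired with each ADA sample even if PK sampling is otherwise cut under footnote i.

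Inconclusive participants should not be dropped. Positives would always count, while negatives would count only once drug had cleared. In the 18.5-day case the expected Day 57 level at 5.4 mg/kg is above any tolerance of 1 to 5 ug/mL. With, say, 1 positive among 6 active, dropping the other 5 gives 1/1 = 100%, and with no positives it gives 0/0. The two-way report gives 1/6 to 6/6, which states the uncertainty honestly. Dropping them from the PK comparison would also select on exposure, the quantity being compared.

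The cost is SAP wording, one merge of ADA and PK data already scheduled, and minor extra tables. The incidence range at the top doses will be wider if drug tolerance is low. If late drug levels are low, almost nobody is flagged and the report shows that the negatives are credible.
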